1.2 STUDY DESIGN

1.3 SCHEDULE OF ACTIVITIES (SOA)

		Day of surgery			
Procedures	Screeninga	Pre-dose	First dose	Second dose	Limbal
		Pre-dose	-90 (±15) min	-60 (±15) min	Paracentesis
Informed consent	Χ				
Demographics	Χ				
Medical history	Χ				
Concomitant medications	Χ	Χ			
Pachymetry	Χ				
Fluorescein test	Χ				
Inclusion/Exclusion	Х	Х			
criteria	Χ	Α			
Pregnancy test ^b		Χ			
Randomization		Χ			
Study drug administration ^c			Х	X	
Limbal paracentesis					Х
Administration of					Х
Mydrane ^{®d}					^
Adverse event review and	Х	Х	Х	X	Х
evaluation ^e	^	^	^	^	^

^a Screening must take place not more than 28 days prior to surgery.

^b Urine pregnancy test (women of childbearing potential).

 $^{^{\}rm c}$ Two doses 30 minutes apart, the first 90 (\pm 15) minutes prior to surgery, and the second 60 (\pm 15) minutes prior to surgery.

^d Mydrane[®] is to be administered following withdrawal of aqueous humour.

^e Adverse events are to be reported until 7 (for non-serious AEs) or 30 days (for SAEs) after the last day of study participation.

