4 STUDY DESIGN

4.1 OVERALL DESIGN

This is a randomized, assessor-blinded, parallel-group clinical study.

One hundred and twenty (120) patients scheduled for cataract surgery at 2 centres who have provided written informed consent will undergo screening procedures during a preoperative visit. Prior to surgery, and once eligibility criteria have been confirmed, eligible patients will be assigned to one of the three following treatment groups in a 1:1:1 ratio:

- Levofloxacin 5 mg/ml + dexamethasone 1 mg/ml (test drug)
- Levofloxacin (Oftaquix®)

• Dexamethasone (Tamesad®)

Administration of study drugs will be performed by qualified health care personnel using a micropipette and dispenser. Two doses of one of the study treatments will be administered, the first 90 ± 15 minutes prior to surgery, and the second 60 ± 15 minutes before surgery. The two doses must be administered 30 minutes apart. Eye drops are to be administered at the lateral canthus while applying pressure at the medial canthus to prevent drainage of the drug.

Phacoemulsification and limbal paracentesis will be performed by an experienced surgeon. Before the main incisions of phacoemulsification, approximately 0.05 ml of aqueous humour will be drawn from the anterior chamber with a 30-gauge needle syringe. Mydrane[®], a combined solution (phenylephrine [0.31%], tropicamide [0.02%] and lidocaine [1%]) for intracameral injection indicated for cataract surgery to obtain mydriasis and intraocular anaesthesia during the surgical procedure is to be administered following paracentesis. The patient's participation in the study will end with the administration of Mydrane[®]. Following surgery, patients will be treated with antibiotics and/or steroids according to local clinical practice.

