6.4 STUDY INTERVENTION COMPLIANCE

Study personnel will be responsible for respecting administration times and recording them in a Dose and Sampling Log. Compliance will not be evaluated as patients will receive two doses of treatment within the first two hours prior to cataract surgery.

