9.4.3 SAFETY ANALYSES

The incidence of Adverse Events (AEs) and Serious Adverse Events (SAEs) recorded throughout the study will be presented overall and by treatment group respectively.

Depending on the onset date of the event, AEs will be defined as follows:

- Treatment-emergent AEs, those events with an onset date after any treatment initiation.
- Non-treatment-emergent AEs, those events with an onset date between informed consent and any treatment initiation.

Non-treatment-emergent AEs will be listed only.

Sponsor: NTC S.r.l.

Version 1.0

Protocol No.: LevoDesa_05-2017 21 March 2018

Treatment-emergent AEs will be summarized using the Medical Dictionary for Regulatory Activities (MedDRA) System Organ Class (SOC) and Preferred Term (PT). A summary of treatment-emergent AEs by SOC, PT and severity will be also provided. All related treatment-emergent AEs, treatment-emergent AEs with an outcome of death, treatment-emergent AEs leading to discontinuation of treatment will be summarized by MedDRA SOC and PT and will also be listed.

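### Section 9.4.3 sets treatment-emergent status by onset date, but a date comparison cannot separate pre-dose from post-dose events when both fall on the day of surgery

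*Combined protocol and SAP*

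**What the plan says.** Section 9.4.3 opens with a general commitment: "The incidence of Adverse Events (AEs) and Serious Adverse Events (SAEs) recorded throughout the study will be presented overall and by treatment group respectively". It then introduces the classification with "Depending on the onset date of the event, AEs will be defined as follows" and gives two classes:

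- The class that goes into the tables is worded as "Treatment-emergent AEs, those events with an onset date after any treatment initiation".
- The class for earlier events is worded as "Non-treatment-emergent AEs, those events with an onset date between informed consent and any treatment initiation".

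The second class gets no tables: "Non-treatment-emergent AEs will be listed only". The first class is tabulated by MedDRA System Organ Class and Preferred Term (SOC/PT) and by severity. Related events, events with a fatal outcome and events that stop treatment are summarised separately.

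On timing, the Schedule of Activities (1.3) puts the pre-dose check, the two doses and the paracentesis under one heading, "Day of surgery". Section 6.4 says that "patients will receive two doses of treatment within the first two hours prior to cataract surgery", and Section 4.1 says that the patient's "participation in the study will end with the administration of Mydrane", which follows the paracentesis.

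**The concern.** In a trial lasting weeks, an unresolved tie on the first dosing date touches few events. Here the dosing date is the whole of study participation after screening. A rule that works on dates therefore leaves open the one day on which dosing takes place and on which every scheduled post-dose AE review falls.

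At stake is the content of the treatment-emergent tables. They could omit events that begin between the first instillation and midnight, or they could include events that began before any drug was given. Section 8.3 rests the safety assessment entirely on adverse events, so the rule that decides which of them are tabulated should be unambiguous before database lock.

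**Working it through.** The plan states no figure on this point, so the check sets the definition against the schedule.

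**Inputs**

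- Classifying variable: onset date (9.4.3).
- First dose at 90 ± 15 minutes and second dose at 60 ± 15 minutes before surgery, 30 minutes apart (6.1.2).
- AE review is marked at five points: screening, pre-dose, first dose, second dose and paracentesis (1.3). Four of the five are on the day of surgery.
- Reporting window after the last day of participation: 7 days for non-serious AEs, 30 days for SAEs (1.3, 8.4.4).
- Time of onset is an AE data item (8.4.4). Administration times go into the Dose and Sampling Log (6.4).

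**Step 1: three ways to apply the rule.** Let D be the date of first instillation and T its clock time.

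| Event | Onset date > D | Onset date ≥ D | Onset date-time ≥ D, T |
|---|---|---|---|
| On D, before the first dose | not treatment-emergent (correct) | treatment-emergent (wrong) | not treatment-emergent (correct) |
| On D, after the first dose | not treatment-emergent (wrong) | treatment-emergent (correct) | treatment-emergent (correct) |
| After D, within the window | treatment-emergent (correct) | treatment-emergent (correct) | treatment-emergent (correct) |

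Each date-only version misplaces one kind of dosing-day event. Only the date-time version places all three correctly.

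**Step 2: what the later-than-D version would leave.** The reviews at the second dose and at the paracentesis are both on D, so no event with onset by the last scheduled contact could be treatment-emergent. The tables would hold only events starting from the next calendar day. Those start after surgery and, where given, after the local-practice antibiotics or steroids mentioned in 4.1.

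**Step 3: consistency with a planned table.** Section 9.4.3 plans a summary of treatment-emergent AEs that lead to stopping treatment. Treatment is two doses 30 minutes apart, so such an event must begin after the first dose and before the second was due, and hence on D. Under the later-than-D version this table is empty by construction.

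**Step 4: length of the gap, for illustration.** The documents do not give surgery times. Assume surgery between 09:00 and 15:00 and a first dose 75 to 105 minutes earlier. Hours from first dose to midnight = 24 − (surgery hour − minutes/60).

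- Longest: 24 − (9 − 105/60) = 16.75 hours.
- Shortest: 24 − (15 − 75/60) = 10.25 hours.

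On that assumption, the later-than-D version excludes roughly the first 10 to 17 hours after dosing.

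**Step 5: missing times.** Section 9.4.1 says that missing values are not replaced, and 9.4.3 gives no default for a dosing-day event without an onset time.

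**The case against.** The best answer is that initiation is a moment, not a date. The text says after treatment initiation, not after the date of initiation, and a reaction minutes after instillation is after initiation in ordinary language. Onset date may simply name the onset variable, since 8.4.4 uses both time of onset and onset dates for the same AE data. A programmer with both times available would probably compare them. This stands as a plausible reading and is why misclassification is a risk rather than a certainty. It does not remove the gap, because 9.4.3 never says that clock times will be used and names the onset date each time it classifies.

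Three stronger conclusions might be inferred, and the documents do not support them:

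- That same-day reactions vanish from the AE reporting. The first sentence of 9.4.3 covers all AEs and SAEs recorded, by group, with no treatment-emergent restriction, and 9.4.7 provides patient listings.
- That the text assigns post-dose events to the listing-only class. That class requires an onset between consent and initiation, which does not clearly describe an event after instillation. The dosing date is left unassigned.
- That pre-dose events would be treated as caused by the drug. Treatment-emergent status is about timing; causality is a separate clinical judgement (8.4.3.2).

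It is also fair that safety is not the study endpoint (Section 3) and that all analyses are descriptive (9.1). No endpoint result depends on this label.

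**Conclusion.** The point holds as a minor but real defect of wording. The stated date rule cannot order events within the day of surgery, and each date-only reading misplaces one kind of same-day event. The exposure is confined to the treatment-emergent summaries: SOC/PT, severity, related, death and discontinuation. The overall by-group incidence and the listings are unaffected.

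The number of events cannot be sized, because the documents give no AE rate for the day of surgery. A claim that all dosing-day events would be lost assumes the strictest reading and is not shown by the text. The conclusion rests on two assumptions: that 9.4.3 is programmed as written, on dates, and that no analysis document outside those reviewed adds a time rule.

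**What to change.** Replace the definition in 9.4.3 along these lines: an AE is treatment-emergent if its onset date and time are at or after the time of first instillation recorded in the Dose and Sampling Log, within the existing reporting window of 7 days (30 days for SAEs). Add that an event on the dosing date with a missing onset time is counted as treatment-emergent, and define the non-treatment-emergent class as onset after consent and before that instillation time.

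The cost is a short text change before database lock, plus one data check. Section 10.1.6 lists the Dose and Sampling Log as a source document, but the documents do not say that its times are entered in the eCRF. The sponsor should confirm that they reach the analysis database and add the field if they do not. No change to the design or visits is needed.

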8.4.4 TIME PERIOD AND FREQUENCY FOR EVENT ASSESSMENT AND FOLLOW-UP

The occurrence of an adverse event (AE) or serious adverse event (SAE) may come to the attention of study personnel during study visits and interviews of a study participant presenting for medical care, or upon review by a study monitor.

All AEs including local and systemic reactions will be captured on the appropriate case report form (eCRF). Information to be collected includes event description (a diagnosis and not symptoms should be provided, if possible), time of onset, clinician's assessment of severity, relationship to study product (assessed only by those with the training and authority to make a diagnosis), and time of resolution/stabilization of the event. All AEs occurring while on study must be documented appropriately regardless of relationship. All AEs will be followed to adequate resolution.

Any medical condition that is present at the time that the participant is screened will be considered as baseline and not reported as an AE. However, if the study participant's condition deteriorates at any time during the study, it will be recorded as an AE.

Changes in the severity of an AE will be documented to allow an assessment of the duration of the event at each level of severity to be performed. AEs characterized as intermittent require documentation of onset and duration of each episode.

The investigator will record all reportable events with onset dates occurring any time after informed consent is obtained until 7 (for non-serious AEs) or 30 days (for SAEs) after the last day of study participation. Events will be followed for outcome information until resolution or stabilization.

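### Treatment-emergent AEs are defined by onset date alone, so an AE that starts between screening and dosing and worsens after the eye drops is left out of the treatment-emergent tables

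*Combined protocol and SAP*

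**What the plan says.** Section 9.4.3 sorts adverse events on a single criterion: "Depending on the onset date of the event, AEs will be defined as follows". The two classes are "Treatment-emergent AEs, those events with an onset date after any treatment initiation" and "Non-treatment-emergent AEs, those events with an onset date between informed consent and any treatment initiation". For the second class, "Non-treatment-emergent AEs will be listed only". The summaries by SOC and PT, by severity, of related events, of events with a fatal outcome and of events leading to treatment discontinuation are each specified for treatment-emergent AEs.

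The same section opens with a wider statement: "The incidence of Adverse Events (AEs) and Serious Adverse Events (SAEs) recorded throughout the study will be presented overall and by treatment group respectively". That sentence is not confined to treatment-emergent events.

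Section 8.4.4 governs recording. AEs are collected from informed consent. A condition already present at screening is baseline, but if the participant's "condition deteriorates at any time during the study, it will be recorded as an AE". For an AE that is already running, "Changes in the severity of an AE will be documented to allow an assessment of the duration of the event at each level of severity". Intermittent AEs have onset and duration documented for each episode. Section 8.4.6 has progression of an SAE reported as follow-up to the episode first reported, not as a separate event.

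**The concern.** A treatment-emergent definition normally has two limbs: events that begin after dosing, and events that began earlier but became worse after dosing. Section 9.4.3 has only the first. An AE that arises in the days before surgery and intensifies after the study drops is assigned to the pre-treatment class by its start date, whatever happens afterwards.

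Section 8.3 makes adverse events the whole of the safety assessment, so these tables are where a difference in tolerability between the combination and its single components would be seen. Compared with a definition that includes worsening, the onset-only rule can lower the tabulated counts but never raise them.

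**Working it through.** The plan gives no AE rate and no figure for this point, so there is none to reproduce. The check is mainly one of reading the rules together.

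**Step 1: the window.** The Schedule of Activities (section 1.3) allows screening up to 28 days before surgery, and both doses are given on the day of surgery. An AE can therefore start after screening and before the first dose over a period of up to 28 days.

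**Step 2: apply the rules to three continuous events.**

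| Event | Recording rule | Onset used | Class under 9.4.3 |
|---|---|---|---|
| A. Irritation present at screening, worsens after dose 1 | 8.4.4: deterioration of a baseline condition becomes an AE | Post-dose, if dated at the worsening | Treatment-emergent, tabulated |
| B. Irritation starts after screening, mild before dosing, severe after dose 1 | 8.4.4: severity change documented within the AE | Pre-dose, if it stays one event | Non-treatment-emergent, listing only |
| C. Irritation starts after dose 1 | Ordinary new AE | Post-dose | Treatment-emergent, tabulated |

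The onset in row A is an inference, because 8.4.4 does not say how a deterioration is dated. The onset in row B is also an inference, but two passages support it: tracking how long the event lasts at each severity level implies one event with several levels, and 8.4.6 treats SAE progression as part of the same episode.

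**Step 3: look for a rule that rescues B.**
- The deterioration rule in 8.4.4 follows on from conditions present at screening. B was not present then.
- The rule for intermittent AEs dates each episode, so a fresh post-dose episode may be captured. B is continuous.
- Recording exact onset times would not help, because B starts before the first dose at any resolution.
- Sections 8.4.1, 8.4.5 and 9.4.3 contain no worsening clause.

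**Step 4: size per patient.** Section 9.2 plans 40 patients per arm. One patient moved in or out of a table row changes that arm's incidence by 1/40 = 0.025, or 2.5 percentage points. This is an upper figure in that it assumes the patient has no other event in the same row. It also assumes that all 40 are dosed, since the safety population in 9.3 is dosed patients.

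**Step 5: number of patients.** This rests entirely on assumed rates. Let p1 be the proportion with an AE that starts before dosing and is still ongoing, and p2 the proportion of those that worsen after dosing. The expected number is 120 × p1 × p2, and the chance of at least one is 1 − (1 − p1 × p2)^120.

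| Assumed p1 | Assumed p2 | Expected patients | Chance of at least one |
|---|---|---|---|
| 2% | 10% | 0.24 | 21% |
| 5% | 20% | 1.2 | 70% |
| 10% | 50% | 6.0 | 99.8% |

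The range is 25-fold. It shows that the number cannot be fixed from the documents, and no row should be read as a forecast.

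**The case against.** The strongest reply has four parts.

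1. **The events do not vanish from all by-arm reporting.** A reader might infer that an event like B drops out of every by-group safety table. The documents do not support that. The opening sentence of 9.4.3 promises by-group incidence of AEs and SAEs over the whole study, and on its own terms could include B. A fatal worsening would be an SAE and could be counted there even while missing from the fatal treatment-emergent table. This stands, and it limits the claim to the treatment-emergent tables. It does not remove the problem: the sentence sits uneasily with the listing rule, and a whole-study count would not show that the event worsened on treatment.

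2. **The onset dates in A and B are not stated.** A reader might infer that the plan demonstrably scores identical worsening in opposite ways. The protocol does not say whether a worsening opens a new eCRF entry with its own onset date. If sites did that, B would be captured. This stands as a caveat. The single-event reading is the natural one, not an explicit rule.

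3. **The affected set is narrow.** The event must start after screening, persist to dosing and then worsen. Eligibility is rechecked before dosing (section 8.1), treatment is two doses on one day, and most of the follow-up falls after surgery, which can itself worsen an ocular event. This stands and keeps the likely number small. It does not make the number zero: the fluorescein test is scheduled only at screening, non-ocular AEs are largely untouched by the eligibility criteria, and recording continues for 7 days (30 for SAEs) after participation ends.

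4. **Nothing is lost and nothing depends on it.** Listings are provided, SAEs are reported within 24 hours whatever their cause, the only endpoint is aqueous humour concentration, and the analysis is descriptive. This is correct. What is affected is tabulation, not capture or safety reporting.

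**Conclusion.** The point holds in a limited form. Section 9.4.3 has no worsening limb. On the natural reading of 8.4.4 and 8.4.6, a continuous AE that starts between screening and the first dose and worsens after dosing is excluded from all the treatment-emergent summaries. Its place in the overall by-group incidence is unresolved, because two sentences of the same section conflict.

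The effect is up to about 2.5 percentage points of an arm's incidence per affected patient, given 40 dosed patients per arm. How many patients would be affected cannot be derived from the documents. A reader might take the 70% in the middle row of the second table as the likelihood that the trial misclassifies someone; it follows only from the assumed 5% and 20%, for which the documents give no support.

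Concentration results and sample size are unaffected. The correction is worth making because the stated rule undercounts in one direction and is cheap to repair, not because the trial's objective is at risk.

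**What to change.** In section 9.4.3:

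- Define treatment-emergent AEs as events with onset after the first dose of study treatment, or with onset before the first dose and an increase in severity after it.
- Tabulate a worsened event at its worst post-dose severity.
- Restrict the non-treatment-emergent class to events that start before the first dose and do not worsen after it.
- Reconcile the opening sentence with the listing rule, by saying whether the overall by-group incidence covers all AEs since consent or only treatment-emergent ones.

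It would also help for 8.4.4 or the eCRF completion guidance to state how a worsening is recorded and dated, so that events A and B are handled alike.

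The cost is a short text change and one extra condition in the AE derivation program. The severity changes that 8.4.4 already requires supply the data. The drawback is that some pre-dose events that worsen because of surgery, not the study drug, will enter the treatment-emergent tables. The investigator's relatedness assessment, already collected, can help in reading them.

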9.4.4 BASELINE DESCRIPTIVE STATISTICS

Medical history will be described according to SOC and PT using MedDRA and will be presented by treatment group.

Previous/concomitant medications will be described according to ATC 2 level and PT using the World Health Organization Drug Dictionary (WHO-DD) and will be presented by treatment group.

9.4.5 PLANNED INTERIM ANALYSES

Not applicable

9.4.6 SUB-GROUP ANALYSES

No sub-group analysis is planned.

9.4.7 TABULATION OF INDIVIDUAL PARTICIPANT DATA

Patient listings will be provided.

